6.2 Method of Assigning Participants to Interventions

After being fitted with an automatically recording electrocardiographic monitor, the HGNS device will then be "on" versus "off" (where "off" is turning off the HGNS device for one night and "on" is turning on the HGNS device) over the ensuing 14 days. Participants will be randomized to "off-on" versus "on-off" periods, assuring no more than two consecutive days of either device use or not—this helps assure equal or nearequal days for each assignment even with truncated follow-up; and maximizes the number of switches between the two to assure examination of acute effects rather than chronic, cumulative effects.

6.3 Measures of Intervention Compliance

Compliance with intervention assignments will be assessed based on review of daily reports. These reports could be accessed through the Inspire® app that allows patients to share sleep therapy data with their clinicians, or alternatively, downloaded during a clinic visit.

7 STUDY PROCEDURES

7.1 Participant Recruitment

Potential participants will be referred to us from the UCSF Sleep Surgery Division where >200 patients with HGNS therapy are being followed (and implants continue to be placed). Research personnel will contact these potential participants to schedule an initial in-person Enrollment Visit at Parnassus, or for a remote Enrollment Visit via video conference, with a study coordinator. During the Enrollment Visit, study staff will confirm that the participant is eligible for the study via an eligibility survey. Study staff will then review the study terms and obtain informed consent from eligible, interested participants. Study participation is anticipated to be 16 days with two in-person or remote visits occurring at study commencement and termination (Baseline and Termination). The participant may withdraw voluntary participation at any time. An early termination visit should be done if a participant chooses to discontinue participation prior to study completion.

7.2 Mobile Study Activities: Mosio for Research

We will use the Mosio platform, a text messaging software that connects to REDCap for digital surveys, to facilitate single subject case-crossover experiments.

7.3 ECG Monitor: ZIO® XT Patch Event Monitor

Each participant will be equipped with a ZIO® XT Patch (iRhythm, San Francisco), which is a 2" by 3" sticky patch. This external cardiac event monitor utilizes validated

algorithms to automatically detect heart rhythm disturbances independent of heart rate. The device records every heartbeat, providing a continuous Holter function. The ZIO® XT Patch is produced by iRhythm and mailed in a prepaid box back to iRhythm for analysis. iRhythm will not receive any patient identifying information.

7.4 Home Sleep Apnea Test

Each participant will undergo two consecutive days of home sleep apnea recording using the WatchPAT® ONE-M Home Sleep Apnea Test (Itamar Medical, Caesarea). The WatchPAT® ONE-M is a disposable, portable, home sleep apnea test and diagnostic device that uses peripheral arterial tonometry, an approved measure that has an 89% correlation with polysomnography, the reference standard to diagnose and assess the severity of OSA.²⁵ We will collect data on the Apnea/Hypopnea Index (AHI), the number of apnea episodes throughout the night, pulse oximetry and heart rate. The manufacturer, Itamar Medical, will not receive any patient identifying information.

7.5 Text Messaging Service

We will use Mosio, text messaging software for clinical research that will deliver daily text reminders with surveys to the participants. Participants will receive a text welcoming them to the study upon completing the Enrollment and Baseline Visits, and daily texts with relevant study surveys throughout the monitoring period.

7.6 Enrollment Visit (Pre-Screening/Pre-Consent)

The Enrollment Visit (on or before Day 0) takes place on the same day as or prior to the day of the Baseline Visit and is aimed for:

- Pre-screen potential participants by eligibility criteria
- Schedule Baseline Visit

At this point, participants are still free to use their HGNS as usual.

7.7 Baseline Visit (Before Day 1)

Study staff will meet the study participant at UCSF (i.e. in the Clinical Research Center) or remotely through a phone/video call. If the participant is eligible per the study's inclusion and exclusion criteria, the study staff will review and obtain informed consent

At this visit, the study staff will also collect the participant's contact information. Additionally, the study staff will administer baseline surveys including demographics, bits (such as alcohol, smoking, cannabis use), medical conditions, medications inventory, Epworth Sleepiness Scale, Insomnia Severity Index and Functional Outcomes of Sleep Questionnaire.

At the Baseline Visit, the study staff, all of whom are trained, will fit the provided devices for an in-person participant or direct self-administration for a remote participant, and instruct the participant on device application and care. The study staff will inform the participant of relevant risks pertaining to potential skin irritation from the adhesive on the devices and will also explain relevant information pertaining to loss of privacy in the study (see section 8.1).

After completion of study device education and fitting, the study staff will schedule the participant's final Termination Visit (Day 15+). Participants are still free to use their HGNS device as usual on the day of the Baseline Visit.

7.8 Randomization and Monitoring (Day 1-14)

At 08:00 AM on the first day (Day 1), the participant will receive a text or push notification from a mobile app or text messaging service with instructions for the same day's randomization. Their first reminder regarding their randomization will be at 08:00 PM on Day 1. During the study (Day 1-14), participants will receive two text or push notifications (AM and PM) each day:

- 1. 08:00 AM: Instructions on the present day's randomization, in addition to daily surveys on randomization compliance and sleep quality.
- 2. 08:00 PM: Reminder of instructions on the present day's randomization.

At 08:00 AM on Day 15 participants will complete the final compliance survey and will be reminded to resume their normal HGNS use.

"On" day messages will instruct participants to use their HGNS device and on "off" days, participants will be instructed to not used them. To avoid >2 consecutive days with or without using their device, participants will be randomized in pairs of either "off one day and on the next day" or "on one day and off the next day".

Each participant will also undergo two consecutive days of home sleep apnea recording using the WatchPAT® ONE-M Home Sleep Apnea Test, ideally during the first days of participation.

Throughout the study period (Day 1-14), the participants should continuously wear their ECG monitor.

7.9 Assessment of sleep quality

The sleep quality on the preceding night will be assessed via a mobile app-based survey and categorized as "amazing," "good," "average," "bad," or "horrible." As previously reported, the choice of terminology and method of data input were developed in collaboration with patients to prioritize capture of information believed in their opinion to be important, maximize ease of understanding, and facilitate daily use.⁹

7.10 Monitoring Close-Out Visit (Day 15+)

During the Termination Visit (Day 15+) on Day 15 or later, the study staff will meet the study participant at UCSF (i.e. in the Clinical Research Center) or remotely via phone/video call at the time specified by the study participant. The study staff will remove or remotely instruct the participants on how to remove the ECG monitor.

8 RISK AND BENEFIT ASSESSMENT

8.1 Risks

Potential risks of the study include the following:

- *Small risk of loss of privacy*: Data that the participant provides to the study may be sensitive and could be embarrassing to participants or lead to insurance coverage problems if it were leaked (e.g., obesity or very high blood pressure).
- *Financial risk*: Participating in the study may make participants want to access the healthcare system more often or purchase health-related devices to link to the study, and that all costs money.
- *Risks of study sensors*: Allergy to the adhesive used for the event monitor electrodes can lead to a rash, pruritus, and/ or painful irritation. Topical steroids will be provided if needed and participants will be provided an option to decline if they are concerned given past experience. As with previous studies, sensors may be moved and/ or not worn if irritation is not tolerable (in which case, late screenfailures and alternative/ additional participants may be used for replacement).
- Risks of HGNS withdrawal: as expected participants may experience an increase in sleep disruption on the days their device is off, potentially leading to a relapse of their OSA symptoms. There should be no long-term effects of therapy withdrawal. Indeed, a previous study showed that 1-week continuous withdrawal of therapeutic HGNS results in acute worsening of both objective and subjective measures of sleep and breathing, but with return of the positive therapeutic effects upon resuming therapy. To limit the acute negative impact of the withdrawal therapy on their well-being, no participant will be instructed to turn off their device more than 7 out of the 14 participation days. It is also part of standard of care

8.2 Benefits

There are no direct benefits for participating in this study. However, the knowledge gained from this study may help better understand the mechanisms underlying AF occurrence. Furthermore, compelling evidence of the direct impact of sleep disruption on discrete AF episodes would be directly and immediately relevant to clinical care of patients with AF.

8.3 Assessment of Potential Risks and Benefits

The Investigator considers protection against risks to be a major responsibility. The following strategies are pursued to minimize risks:

- Risk of loss of privacy: Storage of study data in a secure database.
 - o Password-protected log-in will be required to see study data. A password recovery system will be set up to allow participants to input both the question and answer for a "hint" that can be provided by the website.
 - o An explicit Privacy Statement is included in the Informed Consent document and posted to the study website to fully inform participants.
 - An audit trail will record all logins and any changes to study data.

- o If an event occurs that threatens participant privacy or data security, we will notify our IRB immediately and fully document the occurrence.
- E-mails, app notifications, and texts to the study participants are for the sole purpose of engagement and retention. No sensitive health information will be sent via e-mail to a participant.
- Financial risk: Participants are informed about the financial risk and encouraged not to see a healthcare provider (for which they might have to pay) solely for the purpose of collecting data for the study.
- Online surveys and linkage to health data from sensors or web applications: Study coordinators are available (by email and by phone) to answer any uncomfortable questions about surveys, study devices, or other study activities that arise.
- *Risks of study sensors:* Hypoallergenic adhesive will be provided to patients that develop any rash, pruritus, or painful irritation that develops. Participants will also be prescribed oral Benadryl and/ or topical steroid cream if necessary. Finally, they will have the option to discontinue participation if an adhesive reaction is not tolerable.
- Risks of HGNS withdrawal: The study is designed specifically to avoid participants to have their device turned "off" more than 7 out of the 14 participation days, with no two consecutive days "off". This will be accomplished by a randomization to "off-on" versus "on-off" days. As part of routine clinical care, it is also not uncommon to adjust days on and off to help address variable tolerance of the device use for patients with these implants. Patients also in the course of their clinical care may opt to turn the device off on some nights (such as for comfort) as part of their routine clinical care.

The Investigators have weighed the adequacy of protection against the importance of knowledge gained and determined the risks to be justified. Whether sleep disruption can truly result in any given AF event remains unknown—in fact whether AF can be triggered by any modifiable exposure has not yet been proven in a randomized trial. The importance of the knowledge to be gained from this study is therefore two-pronged: first, the acute effects of sleep disruptions are relevant to the third of the US population who have insufficient sleep. Second, understanding the mechanism that results in the initiation of AF episodes, or the development of incident AF is relevant to the rapidly growing and large number of AF patients because it will reveal mechanisms germane to AF itself. All taken together, the minimal risks incurred by study participants are reasonable considering the broadly applicable knowledge to be gained.

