PARTICIPANT SELECTION CRITERIA	 Inclusion Criteria: Age 21 years or older Have a hypoglossal nerve stimulation (HGNS) device implanted for obstructive sleep apnea and followed up at UCSF Are willing to abstain from using the HGNS device for no more than two consecutive days as instructed over the 14-day trial period Able and willing to provide written informed consent Exclusion Criteria: Currently pregnant or trying to get pregnant Are currently taking Class 1 or 3 anti-arrhythmic medications Have a history of permanent AF or expected to have AF throughout the study period 				

Version #: 1.1 Version Date: 03 June 2025 Page 6 of 21

	 Have congenital heart disease Are >40% ventricular paced Are unable to read or sign to provide informed consent 				
STUDY DURATION	Participants will participate for approximately 2 weeks. • Randomization and monitoring: up to 2 weeks.				
PROCEDURE	After being fitted with an automatically recording electrocardiographic monitor, the HGNS device will then be "on" versus "off" (where "off" is turning off the HGNS device for one night and "on" is turning on the HGNS device) over the ensuing 14 days. Participants will be randomized to "off-on" versus "on-off" periods, assuring no more than two consecutive days of either device use or not. Electrocardiographic monitoring data will be used to assess for endpoints.				
PRIMARY ENDPOINT	The daily number of cardiac ectopic beats				
SECONDARY ENDPOINTS	 The daily number of PACs The daily number of PVCs The daily presence versus absence of AF episodes ≥ 30 seconds 				
STATISTICS Primary Analysis Plan	Our primary analyses will employ intention-to-treat principles, examining randomization assignment as the primary predictor.				
Rationale for Number of Participants	Using a two-tailed alpha of 0.05, we estimate we will need 100 participants to have 80% power in intention-to-treat analyses comparing nights on and off HGNS to detect a 2% increase in cardiac ectopy.				

Version #: 1.1 Version Date: 03 June 2025 Page 7 of 21

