3 STUDY DESIGN

3.1 Study Overview

This is a single center, non-blinded, prospective, randomized, case-crossover trial, where 100 participants will be randomized to turning "on" or "off" their hypoglossal nerve stimulation (HGNS) device each day of a 14-day monitoring period. Participants will wear an automatically recording electrocardiographic (ECG) monitor and utilize a text messaging software for surveys and data capture. Participants will also share their sleep information from their HGNS device with the investigators.

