5 PARTICIPANT SELECTION

5.1 Inclusion Criteria

Participants must meet all the following to be eligible:

- Are age 21 years or older
- Have a HGNS device implanted for OSA and followed up at UCSF
- Are willing to abstain from using the upper airway stimulation device for no more than two consecutive days as instructed over the 14-day trial period
- Able and willing to provide written informed consent

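### Section 8.3 credits the paired randomisation with preventing two consecutive off nights, but the synopsis and Sections 5.1, 6.2 and 7.8 allow two, and pairing can produce them

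*Protocol*

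**What the plan says.** Section 8.3 lists the measures taken to limit each risk. For HGNS withdrawal it says the study is designed to avoid the device being off "more than 7 out of the 14 participation days, with no two consecutive days" off, and attributes this to the off-on versus on-off randomisation. That is a maximum off run of one night.

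Elsewhere the limit is two:

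- **Synopsis, selection criteria:** participants must be willing to "abstain from using the HGNS device for no more than two consecutive days".
- **Section 5.1:** the same criterion, "no more than two consecutive days as instructed over the 14-day trial period".
- **Section 6.2** (repeated in the synopsis procedure): allocation is described as "assuring no more than two consecutive days of either device use or not".
- **Section 7.8:** "To avoid >2 consecutive days with or without using their device, participants will be randomized in pairs", each pair being off then on, or on then off.

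Section 8.1 gives only the cap on the total: "no participant will be instructed to turn off their device more than 7 out of the 14 participation days". It says nothing about consecutive nights.

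**The concern.** The same randomisation is credited with two different guarantees. Section 8.3 says it rules out consecutive off nights. Sections 6.2 and 7.8 say it rules out more than two in a row.

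The stricter statement sits in the risk-minimisation text, where readers look for the exposure participants will face. Section 8.1 acknowledges that off nights may bring back sleep apnoea symptoms, and Section 8.3 offers the run limit as a specific protection. If the allocation does not deliver that limit, the risk section understates the consecutive exposure the schedule permits. It also promises more protection than the two-day limit participants must accept under Section 5.1.

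**Working it through.** **Inputs.** There are 14 randomised days (Sections 3.1 and 7.8), which make 7 two-day pairs. Each pair is off-on or on-off (Section 7.8). The protocol does not state whether pair order is drawn afresh for each pair, nor with what probability. The main calculation assumes independent 1:1 draws.

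**The cap of 7 in 14.** Every pair has exactly one off night, so seven pairs give 7 × 1 = 7 off nights in all 2^7 = 128 schedules. This part of Section 8.3 is reproduced.

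**The run limit.** Within a pair, off nights cannot be adjacent. Two adjoin only across a boundary, when on-off is followed by off-on: on, **off, off**, on. A run of three is impossible because each pair contains an on night. The maximum off run is therefore 2, which matches the synopsis and Sections 5.1, 6.2 and 7.8 but not Section 8.3.

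**How often it happens.** A schedule has no off-off run only if no on-off pair is directly followed by an off-on pair. That requires k off-on pairs followed by 7 − k on-off pairs, k = 0 to 7, which gives 8 schedules.

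- At least one off-off run: (128 − 8)/128 = 120/128 = 93.75%.
- Schedules with 0, 1, 2 and 3 runs: 8, 56, 56 and 8. Two or more: (56 + 8)/128 = 50%.
- Expected runs per participant: 6 boundaries × 1/2 × 1/2 = 1.5.

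**Dependence on the unstated rule.** With probability p of one pair order, q = 1 − p and 7 independent pairs, P(no run) = Σ p^k q^(7−k) over k = 0 to 7. With m pairs at 1:1, P(no run) = (m + 1)/2^m.

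| Assumed allocation | At least one off-off run | Expected runs |
|---|---|---|
| 7 independent pairs, p = 0.5 | 93.75% | 1.5 |
| p = 0.4 / 0.3 / 0.2 | 91.9% / 85.6% / 72.0% | 1.44 / 1.26 / 0.96 |
| Pair orders balanced 3:4 within participant | 68/70 = 97.1% | 1.71 |
| Follow-up ends after 4 / 5 / 6 pairs, p = 0.5 | 68.8% / 81.3% / 89.1% | 0.75 / 1.0 / 1.25 |
| One fixed alternating order for 14 days | 0% | 0 |

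The longest off run is 2 in every row except the last, where it is 1.

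**Which rule the text supports.** Section 6.2 says the scheme "maximizes the number of switches between the two". Taken literally, that means strict alternation, with 13 switches in 14 days; independent 1:1 pairs average 7 + 6 × 1/2 = 10. Against this, a two-day limit on both on and off runs (Sections 6.2 and 7.8) would have no purpose under strict alternation, and Section 7.8 gives that limit as the reason for pairing. Section 7.8 also sends instructions for each day's randomisation, and Section 3.1 has participants randomised to turn on or off their "device each day of a 14-day monitoring period". Section 3.1 is weaker evidence, since it does not mention pairs.

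**The case against.** The best defence is that the statements are logically compatible. A design with no two consecutive off nights also satisfies a limit of two, and an eligibility criterion states what a participant must tolerate, not what will happen. If each participant is randomised once to a strictly alternating order, every statement holds, and the switch-maximising remark in Section 6.2 points that way. This stands as far as it goes: the Section 8.3 clause fails only if pair order can vary within a participant. But that reading leaves the stated reason for pairing in Section 7.8 without a purpose, and nothing in the protocol fixes one order per participant.

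A second defence is that little follows from the discrepancy. Total off nights are unchanged. Section 8.1 cites a study of one week's continuous withdrawal in which benefit returned when therapy resumed. Section 8.3 notes that patients sometimes leave the device off in routine care, and the closing risk-benefit judgement does not mention run length. No endpoint, sample size or analysis is affected. All of this is right and limits the weight of the point. The clause may also simply be a slip for a two-day limit, but that would confirm that the text is wrong where it stands.

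Finally, details of sequence generation often belong in a randomisation specification, which is not at hand. That excuses missing detail, but not a stated property that the described mechanism does not guarantee.

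**Conclusion.** The inconsistency is real and should be fixed. Section 8.3 attributes to the randomisation a safeguard that the allocation described elsewhere does not guarantee and that four other places state more loosely. The wording conflict needs no calculation.

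Its practical size depends on an unstated rule: 93.75% of participants with at least one pair of consecutive off nights under independent 1:1 pairs, 72.0% to 97.1% across the other full-length pair-randomised variants examined, and 0% under one fixed alternating order. The cap of 7 off nights in 14 and the maximum run of two hold under all of these, so only the clause excluding two consecutive off nights is in doubt. The consequence is confined to how off nights cluster and how accurately the risk section describes it.

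**What to change.** Reconcile the synopsis and Sections 5.1, 6.2, 7.8 and 8.3:

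1. State one allocation rule, saying explicitly whether each of the seven pairs is randomised independently or each participant follows one fixed order.
2. State one maximum run of off nights, and use it in the eligibility criterion, the allocation text and the risk section.
3. Check that the randomisation program implements that rule and cannot exceed that maximum.

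Which maximum is acceptable is for the investigator and the IRB to decide. The cost is a wording amendment and a program check, with no extra participants or procedures.

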9 DISCONTINUATION AND REPLACEMENT OF PARTICIPANTS

9.1 Early Discontinuation from Randomization

A participant may be discontinued from randomization at any time if the participant or the investigator feels that it is not in the participant's best interest to continue. The following is a list of possible reasons for study treatment discontinuation:

• Participant withdrawal of consent

- Adverse event that in the opinion of the investigator would be in the best interest of the participant to discontinue treatment
- Lost to follow-up
- Early termination of the study (<2 days)
- Positive pregnancy test

All participants are free to withdraw from participation at any time, for any reason, specified or unspecified, and without prejudice.

Reasonable attempts will be made by the investigator to provide a reason for participant withdrawals. The reason for the participant's withdrawal from the study will be specified in the participant's source documents.

